Please note the primary difference between the current proposal and the original application. In the original application, the target site was Gateway Residential Services (GRS). By the end of the study, the facility changed its name to the Caritas ARTS Program. In addition, we added a second site after consultation with the Project Officer, both to ensure we met the pre-specified recruitment target and to enable us to inform the design of a fully powered trial. The two programs are:

Caritas ARTS Program – short term residential facility with 16 beds, average length of stay 6-10 days

Rosecrance Health Network – long term residential facility with 80 beds, average length of stay 30-45 days

C. SPECIFIC AIMS AND DETAILED STUDY METHODOLOGY

1. Specific Aims

The goal of this pilot study is to adapt the delivery of PW for a new population (parents of ASUD preparing for discharge) and new setting (residential treatment), and to obtain initial data on its feasibility, acceptability, and effectiveness. The study began with an open trial of 10 parents to demonstrate feasibility, acceptability, and preliminary evidence of effectiveness over time.

Specific research aims of the protocol are:

Aim 1: To examine the feasibility and acceptability of an adapted PW intervention that includes moderate engagement strategies for parents of ASUD preparing for discharge from residential.

Hypothesis 1a: Adapted PW will be both feasible and acceptable to parents. Feasibility will be indicated by enrollment rates ($\geq 80\%$) and indicators of parent engagement: attendance of ≥ 2 coaching sessions for $\geq 75\%$ of parents, and online usage patterns of 2+ PW logins, viewing of video vignettes embed in text messages, 1+ parent board posts. Criteria for acceptability will be withdrawal rates ($\leq 20\%$), $\geq 80\%$ of ratings on a consumer satisfaction scale in the highest two categories, and positive feedback from exit interviews with parents.

Secondary Aims 2-4: To examine the preliminary effectiveness of the experimental intervention on: substance use outcomes, related high-risk behaviors, and parenting skills (the putative mediators of change).

Hypotheses: At baseline, 6-week follow up, 12-week follow up, and 24-week follow-up, the experimental intervention will demonstrate superior outcomes, relative to treatment as usual on:

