- 2a: indicators of substance use: substance use frequency, severity of substance use symptoms, rates of relapse, and biological markers (i.e., urine drug screens).
- 3a: high-risk behaviors commonly related to substance use: externalizing behavior, sexual risk behavior, school truancy, and criminal behavior.
- 4a: parenting behaviors: parental monitoring and communication, as demonstrated by both parent and adolescent report and observed during an in vivo task.

2. Detailed Study Methodology

STUDY PURPOSE. We are seeking approval to conduct a randomized control trial of 60 parents whose adolescents are preparing for discharge from residential substance use treatment at a new remote site. The goals of this project are to: (1) examine if the adapted intervention and the study assessment procedures are feasible and acceptable to study participants; (2) evaluate the preliminary effectiveness of the adapted intervention.

STUDY POPULATION. We are currently seeking approval to enroll 60 parent-adolescent dyads (i.e., a total of 12- participants) for a randomized trial.

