Retention procedures. At baseline, multiple sources of contact information will be recorded for parents and ASUD to prevent attrition. A demographic form will be administered aloud by a research staff member at Brown via Zoom and information will be obtained and stored in hard copy form in locked filing cabinets in the PI's office at Brown University. Contact information will be updated by periodic phone calls and during assessments. Reminders will be made via phone and mail. The PI will hold weekly case review meetings to review no-shows and outreach attempts, and discuss plans to complete contact with missing participants. Compensation for completion of questionnaires and interviews/discussions escalates slightly from \$40 at baseline, 6 and 12 weeks to \$60 at 24 week followThis compensation schedules recognizes the increased effort associated with scheduling a follow-up and providing a urine screen after the teen has been discharged. We have used these retention procedures (e.g., reminder calls, periodic update calls, escalating compensation) with success in current and prior projects.

Randomization. In the randomized pilot trial, parent-adolescent dyads will be randomized to the adapted PW condition or to residential treatment as usual using urn randomization balanced by biological sex (male vs female), race/ethnicity (White, Non- Hispanic vs Non-White, Hispanic), and days of substance use (1-45 vs 45+). Randomization will be done by the research staff using a randomization spreadsheet immediately at the end of the baseline assessment; condition assignments will then be immediately told to the family. Those assigned to the adapted PW condition will be scheduled for their first remote coaching session approximately 4 weeks prior to discharge (described below).

Protecting confidentiality. Steps taken to protect the confidentiality of participants are detailed in **Section D, “Possible Risks and Anticipated Benefits”** in the paragraphs focused on minimizing risk of loss of confidentiality.

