INTERVENTION. Parents and adolescents will begin to receive the PW intervention shortly after intake. The residential treatment team works with each adolescent's family, insurance provider, and any auxiliary decision makers (e.g., Child and Protective Services, Youth Probation Officers) to devise a preliminary treatment plan and tentative discharge date. All adolescents and parents will receive the standard treatment offered by the residential facility. In addition, they will receive the additional treatment elements below.

Parenting Wisely (PW). PW is a self-administered, interactive, multimedia online program. PW is available in both English and Spanish (Ser Padres Con Sabiduría). In PW, parents view video vignettes of ten common family

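### Site is left out of the urn although the two facilities' average stays differ at least threefold; balance it for dyads still to be randomized and name it in the Aims 2–4 models

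*Combined protocol and SAP*

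**What the plan says.** All references are to the combined protocol and SAP.

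- **Allocation (C.2, Randomization).** Dyads are allocated "using urn randomization balanced by biological sex (male vs female), race/ethnicity" and days of substance use. No other factor is listed. The allocation ratio and urn parameters are not stated.
- **Sites (section B).** Caritas is a "short term residential facility with 16 beds, average length of stay 6-10 days"; Rosecrance is a "long term residential facility with 80 beds, average length of stay 30-45 days". The Inclusion/Exclusion paragraph also refers to a director at each facility. The Study Purpose paragraph, however, describes "a randomized control trial of 60 parents whose adolescents are preparing for discharge from residential substance use treatment at a new remote site", in the singular.
- **Usual care (C.2, Intervention).** "All adolescents and parents will receive the standard treatment offered by the residential facility". Its content is not described for either site.
- **Adjustment (Data Analysis Plan).** Pre-existing differences on any variable are to be controlled, and the Aims 2–4 mixed models list baseline differences between groups as covariates. Site is not named in either place.
- **Aim 1.** Engagement and acceptability rates are compared with fixed cut-offs, for example "attendance of ≥ 2 coaching sessions for $\geq 75\%$ of parents" in Specific Aims, with no breakdown by site and no interval. The Data Analysis Plan sets a different attendance criterion, split into pre-discharge and post-discharge sessions.

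**The concern.** A variable known at enrollment, and likely to be related to outcome, is left to chance in a trial of 60 dyads. Length of stay is the documented difference between the sites. It matters for Aims 2–4 because the main substance use measures look back 90 days, so at the first follow-up the recall window contains a different mixture of pre-admission, in-residence and post-discharge days at each site. Pre-admission days come before randomization and cannot be affected by PW. They add site-dependent noise to the outcome, and if the arms differ in site mix, that noise becomes a chance shift in the estimated effect.

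At stake is the precision of effect sizes from about 50 dyads, which the plan intends to use in sizing a larger trial.

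**Working it through.** **The plan's own figures.** The documents give none for site imbalance. Their planning figures reproduce, taking two-sided alpha of 0.05 (not stated) and power 0.8. For d = 0.3, 2 × (1.960 + 0.842)² / 0.3² gives 175 per group, as stated. For d = 0.5 the same formula gives 63, and the t-based version gives 64, as stated. Sixty dyads with 15–20% loss leave 51 to 48, against the stated 50.

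**Step 1. Is site prognostic?** Inputs: 90-day recall and follow-up at 6, 12 and 24 weeks after discharge (Measures); stays from section B.

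- At 6 weeks (42 days) the window reaches 90 − 42 = 48 days before discharge.
- Short-stay site: 48 − 10 = 38 to 48 − 6 = 42 pre-admission days.
- Long-stay site: 48 − 45 = 3 to 48 − 30 = 18 pre-admission days.
- The sites differ by 38 − 18 = 20 to 42 − 3 = 39 days; the difference at midpoints is 40 − 10.5 = 29.5.
- At 12 weeks (84 days) the window reaches only 6 days before discharge, within the average stay at both sites. At 24 weeks it does not reach discharge. This mechanism is therefore confined to the 6-week visit.

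The Data Analysis Plan mentions a treatment duration of about 3.5 months, which matches neither site. I used the site-specific stays.

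**Step 2. How often would the arms differ?** Assume 30:30 allocation without regard to site and K short-stay dyads among 60. The number X in the PW arm is hypergeometric(60, K, 30), and the arms differ by |2X − K|.

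| K | P(arms differ by ≥ 6) |
|---|---|
| 15 | 0.072 |
| 20 | 0.170 |
| 30 | 0.196 |

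**Step 3. What would that do to the Aims 2–4 effects?** Take K = 20 split 13 versus 7, a difference in share of 6/30 = 0.20.

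- Assumed site gap of 0.5–0.8 SD: unadjusted d shifts by 0.20 × 0.5 = 0.10 to 0.20 × 0.8 = 0.16.
- Standard error of d with 25 per arm: √(2/25) = 0.28.
- In use days at 6 weeks, if teens used on a fraction r of pre-admission days (assumed), the arm difference shifts by 0.20 × 29.5 × r. That is 1.5, 3.0 and 4.4 days for r = 0.25, 0.50 and 0.75.

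The baseline-use covariate does not fully remove this, because two teens with equal baseline use at different sites have different recall windows.

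**Step 4. Aim 1.** With 30 PW parents, the standard error of a 75% rate is √(0.75 × 0.25/30) = 7.9 points. Site-specific rates are not given, so between-site gaps of 20, 40 and 60 points are assumed.

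- The SD of the PW-arm rate due to chance site mix, at 20 short-stay and 40 long-stay dyads, is 1.84/30 × gap = 1.2, 2.5 and 3.7 points. That is about 3%, 11% and 28% of the rate's variance.
- At a 40-point gap and a 30:30 site split, holding the PW arm's site mix exactly proportional changes the probability of passing 75% from 0.512 to 0.507 at a true rate of 75%, and from 0.773 to 0.787 at 80%.
- Moving the enrolled short-stay share from 25% to 50% shifts the rate by 0.25 × gap = 5, 10 or 15 points. No urn controls this.

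**Step 5. What would a site factor achieve?** A multi-factor urn was simulated with one starting ball of each type, one opposite ball added after each allocation, and the most imbalanced urn used (all assumed). Adding site cut the SD of the PW-arm short-stay share from 6.5 to 4.8 points at a 30:30 site split, and from 5.9 to 4.7 points at 20:40.

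**The case against.** The strongest reply is that the plan already covers this. Controlling pre-existing differences on any variable would take in a visible 13 versus 7 site split, and even unadjusted the shift is about half a standard error or less. That largely stands and keeps the point modest. It does not close it: site is not named, what counts as a difference is not defined, and covariates chosen after inspecting baseline imbalance are a weaker safeguard than one fixed in advance.

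A second reply is that 7–20% depends on accrual order, which is not documented. This also stands. Section B says a site was added. If all short-stay dyads were enrolled first, the urn's early self-correction would carry over to site; a simulation with 20 such dyads and assumed factor prevalences gives roughly 3–4%. With interleaved accrual, or the short-stay site last, it gives about 19–20%.

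A third is that section B looks back to the end of the study, so allocation may be complete. Then only the analysis and reporting changes remain available.

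A reader might go further and infer that chance site imbalance could readily flip the Aim 1 verdicts. The documents do not support this. If 90% of long-stay and 50% of short-stay PW parents met the attendance criterion, the PW-arm rate would be 77% with 10 short-stay dyads and 73% with 13. But those rates are assumed and place the expected rate just above the cut-off. At the same 40-point gap, site mix alone carries the expected rate across 75% with probability of only 3–4% when the true rate is 70% or 80%. The Individual Coaching Sessions paragraph also allows remote sessions up to the 6-week follow-up, so a short stay does not by itself prevent attending two. The enrollment rate is fixed before randomization and is not exposed at all.

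A reader might also infer that usual care differs between the sites. That is plausible but not documented; only the difference in stay is.

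**Conclusion.** The omission is real and worth correcting as an inexpensive improvement. The ground for it is Aims 2–4, where the 90-day recall makes site a likely predictor at the 6-week visit. The expected harm is modest: an occasional avoidable shift in d, smaller than its standard error, which the general adjustment rule may or may not catch. For Aim 1, sampling error and the enrolled site mix matter more than chance imbalance between arms, so reporting by site is the useful step there.

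The sizes rest on an assumed 1:1 ratio, 15 to 30 short-stay dyads, allocation unrelated to site, and an assumed site gap. If only one site is randomized, as the Study Purpose wording could be read, the point does not arise.

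**What to change.** 1. **Randomization paragraph and spreadsheet.** Add site as a fourth urn factor, or run a separate urn at each site, for dyads still to be randomized.
2. **Data Analysis Plan, Aims 2–4.** Name site as a fixed covariate in every model, whatever the observed balance.
3. **Data Analysis Plan, Aim 1.** Report the PW-arm engagement and acceptability rates by site with confidence intervals, alongside the pooled rates.
4. **Consistency.** Reconcile the singular site in Study Purpose with the two sites in section B and the Inclusion/Exclusion paragraph. Reconcile the attendance criterion in Specific Aims with the one in the Data Analysis Plan.

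Cost: one spreadsheet column and a few sentences, slightly looser balance on the other three factors, and one model degree of freedom. Items 2 to 4 remain possible if randomization has finished.

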The proposed study will evaluate one potential low cost, low intensity model for delivering parenting skills to parents preparing for their adolescent's discharge from residential substance use treatment. Specifically, this project will adapt the delivery of a computerized parenting intervention (Parenting Wisely; PW) that has preliminary evidence of efficacy in improving parenting skills and reducing youth behavior problems. PW delivery will be adapted for a new population (parents of ASUD preparing for discharge) and new setting (residential treatment), and preliminary data will be obtained on its feasibility, acceptability, and effectiveness. The open trial has been completed and consisted of recruitment, intervention, and assessment procedures with 10 parents to adapt the delivery of PW to include moderate engagement strategies relevant to this population. Initial engagement strategies have been developed based on focus groups and interviews with 13 parents, 11 ASUD, and three staff members and include up to four sessions of individualized coaching that begin prior to discharge (incorporated into standing family appointment times) and the use of technology (e.g., text messaging and an online parent message board) to maintain contact between staff and parents post-discharge.

Use of a low-cost, low-intensity intervention paired with moderate engagement strategies represents a marked change from traditional office-based treatment delivery methods. The approach has the potential to advance public health by: addressing a high-needs population; targeting parenting practices (putative mediators of change) that have been shown to influence ASUD outcomes; working with parents during a critical treatment juncture; improving parental engagement and access to care, and increasing ease of dissemination and implementation.

B. APPLICATION/PROPOSAL FOR FUNDING/SUPPORT

The initial grant awarded by the National Institutes on Drug Abuse proposed two phases – an open trial and a randomized controlled trial. This protocol pertains only to the **randomized control trial** portion of the study procedures proposed in the funding application at a new site.

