FAsTask Video Code. The FAsTask is an interactive family problem solving task that will be used to provide an in-vivo assessment of parenting behaviors. We have limited the assessment to three tasks that align with our primary aims: 1) Limit Setting (parent leads a 5 min discussion about a time they had to set a limit); 2) Substance Use Norms (parent leads a 5 min discussion on family views about substance use); and 3) Monitoring and Listening (teen leads a 5 min discussion on their peers and parent listens and reacts). Co-I [name] has created a structured clinical codebook that defines each item to be coded and gives specific examples of high and low-scoring observations. Interactions will be observed during each phone or video conference assessment and will be audio recorded. Tapes will be coded by raters blind to condition: 20% of tapes will be double coded.

Data Analysis Plan.

All 60 parents will be included in statistical analyses consistent with an intent-to-treat (ITT) model. Prior to the main analyses, we will run descriptive statistics on key variables to examine distributional properties, identify outliers, and transform variables as needed. The two treatment conditions will be compared on all baseline demographic and clinical variables. Pre-existing differences on any variables and any additional treatment received will be controlled in subsequent analyses.

Missing data. GAIN data is entered into the GAIN's proprietary software, which offers instant error checks and validation reports to prevent missing data. Other forms will be entered directly into study laptops using REDCap (Research Electronic Data Capture), a secure web-based application, to reduce missing data and entry errors. Attrition analyses will compare follow-up completers and non-completers on baseline clinical and demographic variables to determine if they differ systematically. If necessary, we will use standard methods of multiple imputation [123] for variables where unplanned missingness is an issue. For each follow-up time point, we will conduct analyses to identify systematic biases that may have arisen due to non-random dropout.

Aim 1. In the RCT, feasibility will be examined via enrollment rates ($\geq 80\%$) and indicators of engagement, with these preliminary targets: attendance of ≥ 3 of 4 coaching sessions pre-

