discharge and ≥ 1 of 2 sessions post-discharge for $\geq 75\%$ of parents, and online usage patterns of 3+ PW logins, 2+ parent board logins, and 2+ hours logged in for $\geq 75\%$ of parents. Criteria for acceptability include withdrawal rates ($< 20\%$), satisfaction ratings ($\geq 80\%$ of CSQ items rated “agree” or “strongly agree”) and positive feedback from the exit interviews with parents and therapists. Criteria will be finalized based on parent and staff feedback in Phase 1.

Aims 2 - 4. The dependent variables (DVs) include substance use (Aim 2), related high-risk behaviors (Aim 3), and parental monitoring and communication (Aim 4, putative mediators). By nature of residential treatment, we expect teens’ level of substance use and risk behavior to start high at intake, drop off for the duration (~ 3.5 months) of treatment and then increase over the follow-up period. Trajectories that begin at baseline would be misleading, since all teens will have a sustained period of abstinence (with minimal variance). We therefore compare trajectories of use over the follow-up period, while controlling for baseline status as covariates.

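### The Aim 1 attendance target in the Data Analysis Plan presumes six coaching sessions when at most four are offered, and it conflicts with Hypothesis 1a; separately, the four-week start rule cannot be met for an average Caritas stay

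*Combined protocol and SAP*

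**What the plan says.** **Number of sessions.** The opening overview says that the engagement strategies "include up to four sessions of individualized coaching that begin prior to discharge". The Individual Coaching Sessions paragraph sets the same ceiling of four, to be used by the follow-up six weeks after discharge. Therapist Training / Supervision also counts four sessions per client.

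**Attendance criteria.** Two are stated, each to be met by at least 75% of parents.
- Hypothesis 1a (C.1 Specific Aims) lists "indicators of parent engagement: attendance of ≥ 2 coaching sessions for" that share of parents, with no split by discharge.
- The Data Analysis Plan, Aim 1, sets engagement indicators "with these preliminary targets: attendance of ≥ 3 of 4 coaching sessions" before discharge. It continues, after the word break, "discharge and ≥ 1 of 2 sessions post-discharge for" the same share. It adds: "Criteria will be finalized based on parent and staff feedback in Phase 1".

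**Start of coaching.** Under Randomization, families assigned to PW "will be scheduled for their first remote coaching session approximately 4 weeks prior to discharge". Section B describes Caritas as a "short term residential facility with 16 beds, average length of stay 6-10 days" and Rosecrance as a "long term residential facility with 80 beds, average length of stay 30-45 days". The Data Analysis Plan, Aims 2-4, assumes a treatment period of about 3.5 months.

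**The concern.** Feasibility is Aim 1; Aims 2-4 are labelled secondary. Coaching attendance is one of the indicators by which feasibility will be judged, and the Sample Size section makes high feasibility part of the case for a larger trial. If two attendance thresholds stand side by side and one does not match the intervention as delivered, whoever writes up the pilot can reach either conclusion from the same attendance log. Choosing between them after the data are in would weaken the feasibility claim.

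The start rule raises a smaller, practical problem. Staff cannot follow it for a typical Caritas family, and the protocol gives no alternative for short stays.

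**Working it through.** **Inputs**
- Sessions offered: at most 4 in total (overview; Individual Coaching Sessions; Therapist Training / Supervision).
- Analysis-plan target: at least 3 of 4 before discharge and at least 1 of 2 after (Data Analysis Plan, Aim 1).
- Hypothesis 1a: at least 2 sessions.
- Start rule: about 4 weeks, or 28 days, before discharge (Randomization).
- Average stays: Caritas 6-10 days, Rosecrance 30-45 days (section B).

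**Step 1. Check the figure of four.** The supervision section equates reviewing 25% of tapes with one session per client: 1/4 = 25%. With six sessions, one tape would be 1/6 = 16.7%. The figure of four is therefore internally consistent everywhere outside the analysis plan.

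**Step 2. Sessions implied by the target.** 4 + 2 = 6, against 4 offered. The minimum needed to pass is 3 + 1 = 4, which is 4/4 = 100% of what is offered. Because the total cannot exceed four, the only passing pattern is three before and one after. Hypothesis 1a needs 2/4 = 50%, in any split.

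**Step 3. Can the verdicts differ?** A parent who attends three sessions in any split, or all four before discharge, meets Hypothesis 1a and fails the analysis-plan target. If every parent attended two or three sessions, 100% would meet the first criterion and 0% the second.

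For a less extreme illustration, assume that each of four sessions is attended independently with probability p. This is an assumption; the documents give no attendance rate. P(at least 2 of 4) = 1 − (1−p)^4 − 4p(1−p)^3, and P(all 4) = p^4.

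| p | At least 2 of 4 | All 4 |
|---|---|---|
| 0.75 | 94.9% | 31.6% |
| 0.80 | 97.3% | 41.0% |
| 0.90 | 99.6% | 65.6% |

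The last column is an upper limit for the analysis-plan target, because the 3/1 split is also required. Across this range the expected share is above 75% on Hypothesis 1a and below 75% on the other.

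**Step 4. Start date relative to admission** (length of stay minus 28 days)
- Caritas: 6 − 28 = −22 and 10 − 28 = −18, so 18-22 days before admission.
- Rosecrance: 30 − 28 = 2 and 45 − 28 = 17, so day 2-17 of the stay.

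**Step 5. Assumed treatment length.** Taking a month as 30 days, 3.5 × 30 = about 105 days. This matches neither site's average.

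**The case against.** The best defence is that the document itself shows which criterion is current. The analysis-plan figures are labelled preliminary and were to be settled from Phase 1. The overview says that the open trial, the first of the two phases named in section B, is complete. Hypothesis 1a fits the four-session intervention and has the lower PW login bar (2+ against 3+). The natural reading is that 1a is the settled version. I accept that as likely, and it means nobody chose a six-session design. It does not remove the problem: both criteria remain in the current text and neither is marked as superseded.

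On timing, it is fair to say that some passages refer to a new site, which may mean mainly Rosecrance, where the rule fits. Section B and the eligibility section nevertheless name both facilities, and enrolment by site is not given.

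Four stronger readings are tempting, and the documents do not support them.
- *The target is impossible.* It is not: three plus one is four. It demands full attendance in one exact split.
- *Caritas families lose coaching.* They need not, since sessions may run until six weeks after discharge.
- *The Randomization and Intervention sections contradict each other on when to start.* The Intervention section says only that PW begins soon after intake. PW includes online modules, with logins created at enrollment, and text messages that begin on enrollment, so coaching can follow later.
- *The pilot hinges on this one threshold.* Attendance is one of several Aim 1 indicators, and the Sample Size section describes a judgement that combines feasibility, acceptability and effect size.

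**Conclusion.** The concern holds in two parts.

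First, the analysis-plan attendance target is wrong as written for a four-session intervention. It requires 100% attendance in a 3/1 split, where Hypothesis 1a requires 50% in any split, and the two can give opposite answers on the same data. This holds at either site and rests only on the stated counts. The percentages in the illustration depend on the independence assumption and are not forecasts.

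Second, the four-week start rule misses an average Caritas stay by 18-22 days, a gap that the qualifier of approximation cannot cover. It fits Rosecrance, though with about two days to spare for a 30-day stay. These figures use average stays, and their practical weight depends on a site mix that is not stated.

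Both parts should be corrected. Neither affects the randomized comparison or the sample size, which do not use the session count.

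**What to change.** 1. **Data Analysis Plan, Aim 1:** delete the 3-of-4 / 1-of-2 attendance target and the 3+ PW login target. Use Hypothesis 1a as the single criterion: at least 2 of up to 4 sessions, held by the six-week post-discharge follow-up, for at least 75% of parents, and 2+ PW logins.
2. **Randomization:** keep the four-week lead and add that, if the expected remaining stay is shorter, the first session is held as soon as possible after randomization. Timing at Rosecrance stays as it is.
3. **Data Analysis Plan, Aims 2-4:** replace the stay of about 3.5 months with the site-specific averages.
4. **Reporting:** tabulate pre- and post-discharge session counts by site, as description. Measures, Feasibility already collects them.

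The cost is wording and one descriptive table, with no new data. The downside is that pre-discharge attendance is no longer a pass/fail criterion.
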